**SUBJECT DEMOGRAPHICS**

0 unresolved comment(s)

Age level of human subjects: (i.e., 6 mths.; 2yrs., etc.)  to **Study Population:**

Describe the characteristics of the subject population, including age range, gender, ethnic background and health status. Identify the criteria for inclusion and exclusion.

Provide the following information:

- A description of the subject selection criteria and rationale for selection in terms of the scientific objectives and proposed study design;
- A compelling rationale for proposed exclusion of any sex/gender or racial/ethnic group;
- Justification for the inclusion of vulnerable groups such as children, prisoners, adults with impaired consent capacity, or others who may be vulnerable to coercion or undue influence.

Please consider these resources:

[NIH Diversity Policy](#)

[FDA Diversity Guidance](#) 

Pregnant women at 6 to 32 weeks' gestational age with a history of OUD (as defined by the DSM-5) who are receiving MAT (with either buprenorphine based products or methadone) and obtaining prenatal care at one of twelve study sites. Study sites are located throughout Central and Eastern Kentucky and have an established relationship with the University of Kentucky through an existing telemedicine network called the Kentucky Angels network.

Study sites include:

1. Ashland, KY - Karen's Place Maternity Center, ARC
2. Bowling Green, KY: Fairview Community Health Center
3. Corbin, KY: Grace Community Women's Health
4. Georgetown, KY: Brightview Health, LLC
5. Georgetown, KY: UK Women's Health Obstetrics and Gynecology – Georgetown
6. Louisville, KY: University of Louisville, HCCP/Prenatal Clinics
7. Middlesboro, KY: ARH Women's and Family Health Center-Middlesboro
8. Morehead, KY: UK Morehead Women's Healthcare
9. Prestonsburg, KY: Frontier Behavioral Health Center, PLLC
10. South Williamson, KY: ARH Women's and Family Health Center - Tug Valley
11. Vico, KY: Primary Care Centers of Eastern Kentucky
12. Pikeville, KY - Pikeville Medical Center

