Telemedicine arm consultations will be provided by study personnel identified within this application including [name], [name] and [name].

**GROUP CARE ARM:** Study participants at the clusters randomized to the "group" arm will receive group care at 2 week intervals initiated from study enrollment. Group care sessions will be led by an on-site perinatal nurse facilitator and a local peer support specialist. The prenatal group sessions will be imparted in a structured fashion with each session lasting for 45-60 minutes. The content matter discussed will follow a rotating curriculum comprising 8 core sessions over a 16 week period, and will be repeated at each study site as long as there are enrolled active study patients. Once a patient is 8 weeks postpartum ,she will be seen monthly until 6 months postpartum. Data will be collected at each visit by trained study site personnel and entered in a secured online database (REDCap).

**TELEMEDICINE ARM:** Study participants at the clusters randomized to the telemedicine arm will receive the intervention through a telemedicine platform as part of the Kentucky Angels telemedicine program. The division of maternal fetal medicine has established a platform for obstetric outreach addressing perinatal issues pertaining to high risk pregnancies across Kentucky. As part of this cluster RCT, participants at study sites randomized to this arm will receive these telemedicine-based consultations with providers from perinatal nurse educators, peer support specialists, and substance abuse counselors at the University of Kentucky every two weeks until 8 weeks postpartum - and then monthly until 6 months post-partum. Should the patient have the need for additional sessions with a specialist, these will be provided . Data will be collected at each visit by trained study site personnel, and entered into a secured online database (REDCap). See data management plan for more information on the data storage.

The supplemental clinical care that patients will consist of a standardized rotating 8 topic patient education curriculum, including the following topics: 1. Treatment Options for Opioid Use Disorder 2. Smoking Cessation 3. Relapse Prevention Education 4. NAS Reduction Education 5. Breast Feeding Support/Education 6. Domestic Violence Education 7. Postpartum Depression 8. Birth Control/Family Planning.

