## SCHEDULE OF STUDY ASSESSMENTS

## ENROLLMENT/INTAKE

1. DSM-5 Criteria for Opioid Use Disorder
2. Edinburgh Depression Scale
3. Fagerstrom Nicotine Dependence
4. GAD-7 (Anxiety)
5. Adverse Childhood Experience (ACE)
6. Abuse Assessment Screen

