## 3rd Trimester

- 1) WHO QoL-BRF (Quality of Life measure)
- 2) Experience of Care and Health Outcomes (ECHO) - modified
- 3) Cornell Health Services Index (CHSI)
- 4) Fagerstrom Nicotine Dependence
- 5) Edinburgh Depression Scale
- 6) GAD-7

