## 6 months Post-Partum

- 1) WHO QoL-BRF
- 2) Experience of Care and Health Outcomes (ECHO) - modified
- 3) Cornell Health Services Index (CHSI)
- 4) Fagerstrom nicotine Dependence
- 5) Edinburgh Depression Scale
- 6) GAD-7
- 7) Ages and Stages

Study participants will be asked to complete surveys in REDCap available on iPads dedicated specifically for this project; however, all participants will have the option to complete hard copies of the surveys if they prefer. Data from surveys completed on iPads will be uploaded directly into REDCap. Devices will be managed by UK Healthcare IT, which already deploys a large number of iPad devices and is very familiar with the security and management requirements of iOS based devices. UK Healthcare IT currently has a management app configured to ensure the security of the devices and to apply sufficient restrictions that the devices cannot be used for unintended purposes. All devices will be stored securely in locked cabinets.

We will be collecting the following maternal data:

1. Prenatal labs
2. Infectious complications
3. MAT program participation rate (by patient)
4. Study program participation rate (e.g. frequency of clinic attendance at telemedicine and/or group sessions);
5. Prenatal care attendance (medical record review).
6. Urine drug screen result on admission to labor and delivery, 3 and 6 months postpartum (obtained from medical records)
7. Smoking status: evaluated through patient interview and Fagerstrom Nicotine Dependence Scale at intake, 3rd trimester, 3 and 6 months postpartum.
8. Addiction severity: DSM-5 Criteria for Opioid Use Disorder at intake
9. Obstetric complications including but not limited to Preterm birth <37 GA, growth restriction (<10%ile), preterm rupture of membranes, preeclampsia, multiple gestation, gestational diabetes, chorioamnionitis, miscarriage, fetal demise, cesarean delivery (medical record review)
10. Overdose tracking (overdose reversal agent needed, admitted to hospital/ED for overdose): patient interview at every visit
11. Health services utilization: Cornell Health Service Index administered in 3rd trimester, 3 and 6 months post-partum
12. Patient experience of care: Experience of Care and Health Outcomes (modified) Survey administered in 3rd trimester, 3 and 6 months post-partum
13. Depression: Edinburgh Postpartum Depression Scale administered at intake, 3rd trimester, 3 and 6 months postpartum

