14. Anxiety: GAD7 administered at intake, 3rd trimester, 3 and 6 months postpartum
15. Quality of life: WHO QoL-BRF administered in 3rd trimester, 3 and 6 months post-partum
16. Mother-Infant dyad status/Foster care requirement: retention of custody evaluated by patient interview at hospital discharge, 3 and 6 months postpartum
17. Maternal breastfeeding status: evaluated by patient interview at delivery, 3 and 6 months postpartum.

We will be collecting the following fetal data:

Fetal size per gestational age; Any genetic or structural anomalies; any other fetal complications.

We will be collecting the following neonatal data, including the following assessments:

Gestational age and weight at birth; 5 & 10min Apgar score; NICU/nursery hospital admission; NAS diagnosis & treatment requirement (primary outcome); NAS medication days; in-hospital growth (birth to discharge per day); other infant morbidities; total hospitalization length of stay; immunization compliance, ED visits, follow up with scheduled pediatric visits.

Data will be obtained via medical record review, patient interview, physician/staff report, review of state Medicaid data, and hospital discharge data by the study site research staff with the oversight of the UK-study team.

We will perform fidelity monitoring of intervention delivery. Research nurses/facilitators (group arm), providers (telemedicine arm), and all study participants will be asked to complete a fidelity form, similar to an evaluation form, at the end of each educational session. We will evaluate intervention fidelity by comparing provider and participant responses. If any discordance is identified between provider and participant responses for a given topic, additional training related to intervention delivery may be required.

In each arm, patients will be randomly selected to participant in a qualitative interview process at each participating site at the time of the 6 month postpartum follow-up. The interviews will be facilitated by Co-I [name], who has extensive experience using qualitative techniques with substance-involved patients in community based and treatment settings, with the assistance of research coordinators trained in qualitative interviewing techniques. Patients will be offered a fifty dollar stipend for their time to participate in the interview. 3 patients will be randomly selected from each participating site for a total of 33 interviews.

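### Quality of life and health-service use have no intake measurement: the first reading is in the 3rd trimester, after sessions have begun for most possible enrolment dates, which costs precision and a direct check on differential recruitment

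*Combined protocol and SAP*

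**What the plan says.** The Schedule of Study Assessments, under ENROLLMENT/INTAKE, lists six instruments. It opens with "DSM-5 Criteria for Opioid Use Disorder" and continues with the Edinburgh, Fagerstrom, GAD-7, Adverse Childhood Experience and Abuse Assessment Screen instruments. The quality-of-life scale first appears under 3rd Trimester ("WHO QoL-BRF (Quality of Life measure"), together with the Cornell index and the modified ECHO survey.

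The numbered list of maternal data in Data Collection & Research Materials agrees. Item 15 reads "Quality of life: WHO QoL-BRF administered in 3rd trimester, 3 and 6 months post-partum" and item 11 reads "Health services utilization: Cornell Health Service Index administered in 3rd trimester, 3 and 6 months post-partum". By contrast, item 13 has "Edinburgh Postpartum Depression Scale administered at intake, 3rd trimester, 3 and 6 months postpartum" and item 14 has "GAD7 administered at intake, 3rd trimester, 3 and 6 months postpartum"; item 7 gives Fagerstrom an intake value as well.

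Subject Demographics admits "Pregnant women at 6 to 32 weeks' gestational age". Under Research Procedures, women at group sites "will receive group care at 2 week intervals initiated from study enrollment", and Study Design gives the same two-weekly start from enrolment for both arms. The Payment section places the prenatal data collection at 28-32 weeks.

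The SAP plans a generalized linear mixed model with superiority tests for secondary outcomes. Its example covariates are socioeconomic status, race, age and addiction severity, to be used if needed. It mentions no baseline value of the outcome, and it does not name quality of life or service use individually.

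**The concern.** For a woman who enrols early, the first quality-of-life and service-use readings come after months of sessions. They are then outcomes under treatment, and using them as a baseline would adjust away part of any effect.

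Two things are at stake. First, sites are randomised, and site nurses then identify and consent women. The Prisoners section already describes the sites as randomised, and Study Design says nurse facilitators are found at sites allocated to the group arm. If the two modes of delivery attract different women, only a value taken before the first session would show it directly on these measures. Second, the participant's own starting value is usually a strong covariate, and the trial gives it up for these two endpoints.

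**Working it through.** **No stated figure to reproduce.** The documents give no power calculation, SD, ICC or effect size. What follows is schedule arithmetic, then an illustration with assumed values.

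**1. Exposure before the first reading.** Inputs: enrolment at 6-32 weeks (Subject Demographics); prenatal collection at 28-32 weeks (Payment); sessions every two weeks from enrolment (Study Design); 8 core sessions over 16 weeks (Research Procedures).
- Enrolled at 6 weeks: 28 - 6 = 22 to 32 - 6 = 26 weeks of sessions first, or about 11 to 13 sessions.
- A full 16-week cycle can be finished before the first reading by a woman enrolled by 28 - 16 = 12 weeks (assessed at 28) or by 32 - 16 = 16 weeks (assessed at 32).
- A woman enrolled at 28-32 weeks could complete the battery close to intake, but nothing requires this to happen before her first session.

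**2. Precision lost.** Inputs: maximum 267 women (application front page); 12 sites, randomised 1:1 within strata (Study Design), so k = 6 per arm and m = 267/12 = 22.25 per site. Assumed: ICC 0.01, 0.05, 0.10; baseline-to-follow-up correlation r = 0.5 to 0.7.

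In SD units, Var(arm difference) = [ICC + (1 - ICC)/m] × (2/k). If adjustment shrinks only the within-site part, by r², then

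proportional reduction = r² × [(1 - ICC)/m] / [ICC + (1 - ICC)/m].

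| ICC | (1 - ICC)/m | Sum with ICC | Within-site share | Reduction, r = 0.5 | Reduction, r = 0.7 |
|---|---|---|---|---|---|
| 0.01 | 0.0445 | 0.0545 | 0.816 | 20.4% | 40.0% |
| 0.05 | 0.0427 | 0.0927 | 0.461 | 11.5% | 22.6% |
| 0.10 | 0.0404 | 0.1404 | 0.288 | 7.2% | 14.1% |

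At ICC 0.05, SE = sqrt(0.0927 × 2/6) = 0.176 SD. Adjustment lowers it by 1 - sqrt(1 - 0.115) = 6% to 1 - sqrt(1 - 0.226) = 12%.

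**3. Detectable difference at ICC 0.05** (80% power, two-sided 5%, t with 10 df: 2.228 + 0.879 = 3.107). Unadjusted: 3.107 × 0.176 = 0.55 SD. Within-site gain only: 0.51 SD (r = 0.5) or 0.48 SD (r = 0.7). If site means correlate over time to the same degree, the whole variance falls by r² (25% to 49%), giving 0.47 or 0.39 SD.

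**4. Sensitivity.** Research Procedures and Resources speak of 11 sites. With m = 267/11 = 24.27, the reduction at ICC 0.05 is 11.0% to 21.5%. The planned-enrolment table sums to 15 + 15 + 503 = 533. With m = 533/12 = 44.42, the reduction is 7.5% to 14.7% at ICC 0.05 and 4.2% to 33.8% over the whole assumed range.

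**The case against.** Much of the case on the other side stands.

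- **Chance imbalance.** A reader might infer that, without a baseline, a difference at follow-up cannot be told from a pre-existing difference between site populations. For chance imbalance the documents do not support that. The sites are randomised, so the post-only comparison is unbiased in expectation, and the SAP's mixed model for clustering carries between-site variation in its standard error. Only selection after allocation could bias the comparison, and nothing in the documents allows its size to be estimated.
- **Not unique to two measures.** The modified ECHO has the same schedule, and the urine drug screen is first listed at labor and delivery admission. ECHO rates care received, so it has no natural baseline.
- **Partial repair is possible.** Intake Edinburgh, GAD-7, Fagerstrom, ACE, abuse screen and DSM-5 data are partial proxies for quality of life. Medical records and state Medicaid data are listed as sources and might supply prior service use, but no pre-enrolment window is specified. The gain over a model already using these proxies would be smaller than the table shows.
- **Size of the gain.** A 25-49% cut in within-site variance is not a 25-49% cut in the variance of the arm comparison unless site means also correlate over time.
- **Late enrolees.** Women enrolled at 28-32 weeks may have a near-intake value. The documents give no distribution of gestational age at enrolment.
- **Status.** The primary outcome is neonatal abstinence syndrome. The Cornell recall window is in an attachment not reproduced here.

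These points limit the size of the concern. They do not supply the missing baseline.

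**Conclusion.** The point holds in a limited form. The assessment schedule and the itemised data list agree that quality of life and service use have no intake value. Except for women enrolled near 28-32 weeks, the first reading is on-treatment. The consequences are lost precision, and no direct way to check or adjust for differential recruitment on these measures in a trial of 11 or 12 sites. The comparison is not thereby invalid.

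The variance of the arm difference could be cut by about 7% to 40%, or 11.5% to 22.6% at ICC 0.05, with 267 women in 12 sites. This rests on assumed ICC 0.01-0.10 and r 0.5-0.7, on only the within-site part shrinking, and on a comparison with no covariates at all. The change is worth making because it is cheap; the primary analysis is not affected.

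**What to change.** Add the WHO QoL-BRF and the Cornell index to the ENROLLMENT/INTAKE list, to be completed before the first session. State in the SAP that the intake value is a covariate when these two endpoints are compared, and that the 3rd-trimester score is not treated as baseline. ECHO need not be added.

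Enrolment appears to be under way, since the recruitment section reports what has been noted among potential participants. Keep women already enrolled without these values in the analysis. Adjust for intake Edinburgh and GAD-7, which are scheduled for everyone. Handle the missing baseline within the mixed model or by multiple imputation, and report its availability by arm. A missing-indicator should not be relied on: a baseline added late is missing by calendar time, and so possibly by site and arm. If enrolment has closed, the values cannot be recovered; report the limitation and use the proxies.

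The cost is some minutes of participant time at a visit that already has six instruments and a gift card, with questionnaires already in use in the study, and a baseline only partly available for earlier enrolees.

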#### Attachments

Attach Type	File Name
DataCollection	Ages and Stages 6 month instrument.pdf
DataCollection	ASQ-3-4-M.pdf
DataCollection	Adverse Childhood Experience (ACE).pdf
DataCollection	Abuse Assessment Screen.pdf
DataCollection	ECHO (Modified).docx
DataCollection	dsm-5-dx-oud-8-28-2017.pdf
DataCollection	WHO QoL-BRF.pdf
DataCollection	Fagerstrom_test.pdf
DataCollection	GAD_with_Info_Sheet.pdf
DataCollection	Edinburgh.pdf
DataCollection	CSI Primary Care version.ACedit.doc
DataCollection	Fidelity Monitoring - Participant Forms.pdf
DataCollection	Fidelity Monitoring - Provider Forms.pdf

#### Resources

Describe the availability of the resources and adequacy of the facilities that you will use to perform the research. Such resources may include:

- Staffing and personnel, in terms of availability, number, expertise, and experience;
- Computer or other technological resources, mobile or otherwise, required or created during the conduct of the research;
- Psychological, social, or medical services, including equipment needed to protect subjects, medical monitoring, ancillary care, or counseling or social support services that may be required because of research participation;
- Resources for communication with subjects, such as language translation/interpretation services.

This study takes place at 11 individual sites throughout Eastern Kentucky. As such, the resources at each may vary slightly. A general list of available resources includes the following:

University of Kentucky College of Medicine will be the primary hub of this study, and as such will be responsible for the storage and processing of data. Computer access, office space, and locked file storage are available for use in the Department of Obstetrics and Gynecology, located on the third floor of Chandler Hospital. Kentucky children's hospital will volunteer resources such as RedCap creation, additional office space, and staff support. Administrative support, accessibility to fax, high-speed copiers, and printers will be provided by the department of Obstetrics and Gynecology. Research coordinators have access to offices that are well-equipped with PC's and laptops for data entry and internet access for transmission of information. All computers are password protected to ensure confidentiality.

All computer related data will be stored securely under the governance of the PI team. All research labs and common equipment areas are fully equipped with standard items for modern molecular biological research.

A dedicated Research Information Services group provides a high-speed, secure network of microcomputers with access to high-quality printing services, and a variety of sophisticated software packages to the research community. Services include data management and storage, information backup, publication and presentation graphic support services, high-definition audio-visual systems, and VPN connectivity to networks outside the organization for collaborative research including Kentucky Children's Hospital Mainframe Information System.

The 11 sites throughout the state will provide office space for those overseeing the work done at the site, in addition to providing staffing to collect data, computer and internet access, and secure file storage methods which, if paper, will include a locked office. Each research nurse will have a password protected computer on which to enter data. Tablets will be used by research participants (UK-issued) for survey completion.

Finally, the University of Kentucky department of Ob/GYN will provide telemedicine access to sites randomized to the telemedicine arm of this study. This will be done through contract, relying on much of the same information set forth in the Kentucky Angels telemedicine project.

Fidelity Monitoring will also be utilized.

### Potential Risks & Benefits

#### Risks

- Describe any potential risks – including physical, psychological, social, legal, ability to re-identify subjects, or other risks. Assess the seriousness and likelihood of each risk.
- Which risks may affect a subject's willingness to participate in the study?
- Describe likely adverse effects of drugs, biologics, devices or procedures participants may encounter while in the study.
- *Qualitative research* - describe ethical issues that could arise while conducting research in the field and strategies you may use to handle those situations.
- Describe any steps to mitigate these risks.

#### Benefits

- Describe potential direct benefits to study participants – including diagnostic or therapeutic, physical, psychological or emotional, learning benefits. This cannot include incentives or payments.
- State if there are no direct benefits.
- Describe potential benefits to society and/or general knowledge to be gained.

Describe why potential benefits are reasonable in relation to potential risks. If applicable, justify why risks to vulnerable subjects are reasonable to potential benefits.

Study participants will not be required to undergo any invasive procedures as part of this study. Given that we are collecting PHI, risks of study participation pertain to breach of patient confidentiality in the event that PHI may be accessed/misused by non study personnel. We are unable to collect anonymized data since an evaluation of the primary study outcomes relies heavily on relevant clinical information that cannot be collected in an anonymized fashion. We have updated the study consent forms to note that women under criminal justice supervision will not have information about participation disclosed to probation or parole and their decision to participate will not affect their status with any criminal justice agency, treatment, parole, or other agency.

The findings of this study will have considerable societal and public health benefits at large. The benefits from the study will also accrue to the study participants in subsequent pregnancies if results from the data analysis were to predict different practice patterns from the current management protocols for prenatal care with a strong emphasis on the inclusion of patient counseling while undergoing MAT for OUD in pregnancy. These potential benefits strongly outweigh the risk of a breach in patient confidentiality, which is mitigated by the precautions above. Participants criminal justice status does not alter risk/benefit ratio.

